7. DISCONTINUATION OF STUDY VACCINATION AND PARTICIPANT DISCONTINUATION/WITHDRAWAL

7.1. Discontinuation of Study Vaccination

A participant's study vaccination must be discontinued if:

- The participant withdraws consent to receive study vaccination.
- The investigator believes that for safety reasons or reactogenicity reasons (eg, AE) it is in the best interest of the participant to discontinue study vaccination.

Study vaccine assigned to the participant who discontinued study vaccination may not be assigned to another participant. Discontinuation of study vaccination is only possible between screening and vaccination.

7.2. Participant Discontinuation/Withdrawal From the Study

A participant will be withdrawn from the study for any of the following reasons:

- Lost to follow-up
- Withdrawal of consent
- Death
- Any AE that requires discontinuation from the study
- Repeated failure to comply with protocol requirements

^a Note: Ocular, topical, or inhaled steroids are allowed.

When a participant withdraws before study completion, the reason for withdrawal is to be documented in the eCRF and in the source document. If the reason for withdrawal from the study is withdrawal of consent, then no additional assessments are allowed.

An early exit visit (by telephone) will be conducted for those participants who are unable to continue participation in the study and withdraw from the study before Day 183, but who do not withdraw consent (see Schedule of Activities). Participants who wish to withdraw consent from participation in the study will be offered an early exit visit (prior to formal withdrawal of consent; by telephone). They have the right to refuse.

Withdrawal of Consent

A participant declining to return for scheduled visits does not necessarily constitute withdrawal of consent. Alternate follow-up mechanisms that the participant agreed to when signing the ICF apply (eg, consult with family members, contacting the participant's other physicians, medical records, database searches, use of locator agencies at study completion) as local regulations permit.

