AEs and special reporting situations, whether serious or non-serious, that are related to study procedures or that are related to non-investigational sponsor products will be reported from the time a signed and dated informed consent form (ICF) is obtained until the end of the study/early withdrawal. Solicited AEs, collected through a participant diary, will be recorded from the time of vaccination until 7 days post-vaccination. All other unsolicited AEs and special reporting situations, whether serious or non-serious, will be reported from the time of vaccination until 28 days post-vaccination. All SAEs, AESIs, and AEs leading to discontinuation from the study (regardless of the causal relationship) are to be reported from the moment of vaccination until completion of the participant's last study-related procedure, which may include contact for safety follow-up. All AEs will be followed until resolution or until clinically stable.

STATISTICAL METHODS

Sample Size Determination

Humoral Immunogenicity Analysis

Immunogenicity assessments will be performed in all participants.

Sample size calculations for the immunogenicity objectives are performed under the following assumptions.

For the humoral immune response in terms of neutralizing antibody GMTs:

- no difference between all adults aged 18 to 59 years (Groups 1 and 3) and adults aged 65 years and older (Group 5) and no difference between high-risk adults aged 18 to 59 years and adults aged 65 years and older (ie, assuming a true GMT ratio of Day 15 [ie, 14 days after vaccination] RSV A2 neutralizing antibody titers equal to 1 for those comparisons, and similar standard deviation)
- a standard deviation of 1.5 at the log₂ scale for VNA A2 on Day 15*
- non-inferiority limit of 0.67 (2/3)
- 1-sided α of 2.5%

For the humoral immune response in terms of neutralizing antibody seroresponse rates (defined as a 4-fold increase from baseline in Day 15 antibody titers):

- Seroresponse rates are assumed to be 85% in all adults aged 18 to 59 years, high risk adults aged 18 to 59 years and adults aged 65 years and older, based on available data from Phase 1/2 clinical studies,
- Non-inferiority margin of 10%
- 1-sided α of 2.5%

In addition:

• a ratio of 1:1:1 for the **active** groups in Cohorts 1, 2, and 3

• hierarchical testing (ie, test first Group 1+3 versus Group 5, if non-inferiority is demonstrated: test Group 3 versus Group 5)

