4. STUDY DESIGN

4.1. Overall Design

This is a randomized, double-blind, placebo-controlled, multicenter, interventional Phase 3 study to evaluate the safety and immunogenicity of the Ad26/protein preF RSV vaccine in adults aged 18 to 59 years, including those who are at high-risk of severe RSV disease. A cohort of adults aged 65 years and older will also be included. A target of 1,113 participants will be enrolled: 385 healthy adults aged 18 to 59 years will be enrolled in Cohort 1 and randomized in a 9:2 ratio to receive Ad26/protein preF RSV vaccine or placebo; 385 high-risk adults aged 18 to 59 years will be enrolled in Cohort 2 and randomized in a 9:2 ratio to receive Ad26/protein preF RSV vaccine or placebo, 343 adults aged 65 years and older will be enrolled in Cohort 3 and randomized in a 45:4 ratio to receive Ad26/protein preF RSV vaccine or placebo (see Table 1). The study vaccine will be administered as a single IM injection.

Participants will be stratified for COVID-19 vaccine administration (3 categories: 1. Janssen COVID-19 vaccine, 2. Vaxzevria[®] [Oxford/AstraZeneca], 3. other vaccine, or no vaccine).

Table 1: Overview of the Cohorts, Groups, and Targeted Number of Participants				
Cohort		Group	N	Day 1 (Vaccination)
1	healthy adults, 18 to 59 years	1	315	Ad26.RSV.preF 1×10 ¹¹ vp + RSV preF protein 150 μg
		2	70	Placebo
2	high-risk adults, 18 to 59 years ^a	3	315	Ad26.RSV.preF 1×10 ¹¹ vp + RSV preF protein 150 μg
		4	70	Placebo
3	adults, 65 years and older	5	315	Ad26.RSV.preF 1×10 ¹¹ vp + RSV preF protein 150 μg
		6	28	Placebo

N = number of participants, vp = virus particles.

In all cohorts, participants will be stratified for COVID-19 vaccine administration.

All cohorts will be enrolled in parallel. Enrollment in Spain will be limited to Cohorts 2 and 3.

Safety and humoral immunogenicity assessments will be performed for all participants (see Section 9.2.1 for the sample size determination).

For a subset of the participants, additional cellular immunogenicity assessments will be performed. This subset will be referred to as the Cellular Immuno Subset and will consist of approximately 63 active study vaccine participants and approximately 7 placebo participants per cohort. The Cellular Immuno Subset will be recruited in specific study sites.

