The study-site pharmacist or qualified individual with primary responsibility for study vaccine preparation and dispensing will be unblinded to study vaccine allocation.

Participants who have had their randomization group assignment unblinded should continue to return for scheduled evaluations.

Participants who withdraw will not be replaced.

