TTS is considered to be an AESI. Thrombotic events and/or thrombocytopenia (defined as platelet count below the lower limit of normal [LLN] range for the testing lab) are considered to be potential AESIs. All AESIs, including potential AESIs, will be reported to the sponsor from the moment of study vaccination until 6 months after the study vaccination (see Section 8.3.6).

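### Section 7.2 withdraws consenting participants for an undefined AE or for non-compliance after a single dose, so active collection of new SAEs ends before the 6-month safety endpoint, and the AESI period is stated inconsistently

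*Protocol*

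**What the plan says.** Protocol Section 7.2 introduces its list with "A participant will be withdrawn from the study for any of the following reasons". Two of the five entries are "Any AE that requires discontinuation from the study" and "Repeated failure to comply with protocol requirements". Withdrawal of consent, loss to follow-up and death are separate entries. Neither of the two is defined further.

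On treatment, Section 4.1 states "The study vaccine will be administered as a single IM injection", and Section 7.1 adds "Discontinuation of study vaccination is only possible between screening and vaccination".

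On what follows, Section 7.2 and footnotes a and b of the Schedule of Activities provide one early exit visit, by telephone, for those who leave before Day 183 without withdrawing consent. Nothing further is scheduled. Section 8.3.1 collects new SAEs up to the last study-related procedure. Section 10.2.5 requires SAEs unresolved at discontinuation to be followed.

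On AESIs, the Synopsis (Safety Evaluations) puts SAEs and AESIs under one limit, "until completion of the participant's last study-related procedure, which may include contact for safety follow-up". Section 8.3.1 says AESIs "will be reported to the sponsor from the moment of study vaccination until 6 months after the study vaccination", and footnote k agrees. SAP Section 5.1.2 closes the follow-up phase and the AESI intervals at the date of last contact for those who discontinue.

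The primary safety endpoint (Section 3) is SAEs and AESIs to 6 months. SAP Section 5.4 bases unsolicited-AE percentages on participant counts, and SAP Section 5.4.1.4 counts a participant who reports no event as having none.

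**The concern.** In a multi-dose trial, withdrawal for an AE at least stops further exposure. Here all exposure has already happened, so after Day 1 withdrawal ends only observation. It ends observation for a reason linked to safety, in people who may still be willing to be contacted, and the planned tables cannot tell unobserved time from event-free time.

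The early weeks matter most. Section 2.2 reports that TTS symptoms after the sponsor's Ad26 COVID-19 vaccine began about 1 to 2 weeks after vaccination, mostly in women under 60, an age range that overlaps Cohorts 1 and 2. Someone withdrawn in the first week could have the exit call before or during that period.

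The protocol retains others whose participation has been disturbed. Under Section 6.3, "Participants who have had their randomization group assignment unblinded should continue to return for scheduled evaluations", and Section 2.3.1 keeps participants who become pregnant in full safety follow-up. Those withdrawn under the two entries in Section 7.2 get less.

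**Working it through.** **1. The plan's own safety figures (Section 9.2.2).** Inputs are 315 active participants per group and 630 pooled.

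- Probability of at least one event is 1 − (1 − p)^n. For n = 315 this is 79.4%, 95.8% and 100.0% at p = 0.5%, 1% and 2.5%. For n = 630 it is 95.8%, 99.8% and 100%. These match Table 6.
- The one-sided 95% upper limit with zero events is 1 − 0.05^(1/n), which is 0.947% for n = 315 and 0.474% for n = 630. These match the stated limits of less than 1% and less than 0.5%.

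**2. Follow-up lost by one participant.** For an exit call on Day 20 (an example), 183 − 20 = 163 days are lost out of 183 − 1 = 182, or about 90%.

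**3. Effect on precision.** The documents give no withdrawal rate by reason, so the share withdrawn, w, is assumed. Each withdrawal is taken as losing the whole window, which is the worst case. Effective n = 315 × (1 − w).

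| Assumed w | Effective n | P(at least 1 event) at a 1% rate | Upper limit, 0 events |
|---|---|---|---|
| 0 | 315 | 95.78% | 0.947% |
| 1% | 311.9 | 95.65% | 0.956% |
| 5% | 299.2 | 95.06% | 0.996% |
| 10% | 283.5 | 94.21% | 1.051% |

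At 10% the loss is 95.78 − 94.21 = 1.57 points. The zero-event limit stays below 1% when n exceeds ln(0.05)/ln(0.99) = 298.07, so 299 participants are needed. That leaves room for 315 − 299 = 16 complete losses per group (5.1%), from all causes.

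**4. Effect on the observed rate.** If those withdrawn have r times the event risk of those who stay, and their events go unseen while they remain in the denominator, the share of events captured is (1 − w)/[(1 − w) + r·w].

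- r = 1: 99%, 95% and 90% at w = 1%, 5% and 10%.
- r = 3 (assumed): 0.99/1.02 = 97.1%, 0.95/1.10 = 86.4% and 0.90/1.20 = 75.0%.

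Informative loss therefore matters more than lost precision. Both values of r are illustrations.

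**5. AESI period for a participant withdrawn on Day 20 with a new thrombosis on Day 40.** Under the Synopsis, reporting ended at the last procedure, which would be the exit call. Under Section 8.3.1 and footnote k the event is reportable. Under SAP Section 5.1.2 the participant's AESI intervals closed at last contact, so a reported event could fall outside them.

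**The case against.** The strongest reply is that the rule is narrower than it looks. A reader might infer that participants must be removed for particular AEs, or that reactogenicity will routinely trigger removal. The documents do not support this: no AE is named, the criterion is circular, and it may be applied rarely. For the same reason they do not show that every such withdrawal is avoidable.

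A reader might also infer that all collection stops at the exit call. It does not. Open SAEs are followed under Section 10.2.5, and Section 8.3.1 has the sponsor evaluate safety information reported spontaneously after the defined period. Section 7.2 bars further assessments only when consent is withdrawn. The last procedure may itself include a safety contact, but that wording is permissive and no such contact is scheduled. Section 7.2's alternate follow-up and Section 7.3's repeated contact attempts deal with people who decline or miss visits, not with people the study withdraws. What remains is the absence of scheduled, active enquiry about new events.

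On AESIs, Section 8.3.1 gives sites an operative 6-month rule, and Section 8.3.6 requires reporting within 24 hours of awareness. It would go too far to say that sites have no instruction. The conflict with the Synopsis and the SAP still has to be resolved.

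Two numerical inferences should be resisted. The 285 evaluable participants in Section 9.2.1 are an immunogenicity allowance, not a forecast of safety follow-up. The less-than-1% statement concerns zero events in general and is not tied to 6-month SAE or AESI follow-up.

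**Conclusion.** The point holds as a gap in safety follow-up and an inconsistency in collection periods. Followed as written, the protocol ends active collection of new SAEs in some participants who have not withdrawn consent, and for one of the two reasons the loss is plainly informative. The SAP then leaves the unobserved time indistinguishable from event-free time.

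Its size cannot be fixed from the documents. Detection probability falls by at most about 1.6 points for withdrawals up to an assumed 10%. Under-ascertainment could be larger if those withdrawn carry higher risk, but no stated figure establishes that. Safety is analysed descriptively, so no formal test is affected.

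It might be inferred that the co-primary non-inferiority comparisons are biased by unequal withdrawal between active and placebo. They are not, because they compare active groups only (Groups 1+3 or Group 3 with Group 5). An exit before Day 15 does forgo that participant's titre, since the exit visit is by telephone, but the step from 285 to 315 per group already allows for such losses. The change is worth making because it is cheap.

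**What to change.** - **Section 7.2:** separate the end of visits and procedures from the end of safety follow-up. State that vaccinated participants who leave for an AE or for non-compliance, and who have not withdrawn consent, continue SAE and AESI collection by telephone at the remaining safety timepoints (Day 29, if not yet reached, and Day 183). Offer the Day 15 sample if the participant is willing.
- **Collection period:** reconcile the Synopsis, Section 8.3.1, footnote k and the SAP Section 5.1.2 intervals for SAEs and AESIs. Make clear that the SAP's date of last contact includes these safety calls.
- **Clinical judgement:** leave the decision on which AEs warrant stopping study procedures to the investigator and sponsor. The change concerns data collection only.

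The cost is wording in the protocol and SAP and at most two calls per affected participant. Day 29 is already a telephone visit. Day 183 is a clinic visit, so a telephone contact in its place would be new for these participants. The small downside is that some calls will go to poorly compliant participants.

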7.2.1. Withdrawal From the Use of Research Samples

Withdrawal From the Use of Samples in Future Research

The participant may withdraw consent for use of samples for future research (refer to Long-Term Retention of Samples for Additional Future Research in Appendix 3). In such a case, samples will be destroyed after they are no longer needed for the clinical study. Details of the sample retention for research are presented in the main ICF.

7.3. Lost to Follow-up

A participant will be considered lost to follow-up if the participant repeatedly fails to return for scheduled visits and is unable to be contacted by the study site. A participant cannot be deemed lost to follow-up until all reasonable efforts made by the study-site personnel to contact the participant are deemed futile. The following actions must be taken if a participant fails to return to the study site for a required study visit:

- The study-site personnel must attempt to contact the participant to reschedule the missed visit as soon as possible, to counsel the participant on the importance of maintaining the assigned visit schedule, to ascertain whether the participant wishes to or should continue in the study.
- Before a participant is deemed lost to follow-up, the investigator or designee must make every reasonable effort to regain contact with the participant (where possible, 3 telephone calls, e-mails, fax, and, if necessary, a certified letter to the participant's last known mailing address, or local equivalent methods. These contact attempts should be documented in the participant's medical records.
- Should the participant continue to be unreachable, they will be considered to have withdrawn from the study.

Should a study site close, eg, for operational, financial, or other reasons, and the investigator cannot reach the participant to inform them, their contact information will be transferred to another study site.

8. STUDY ASSESSMENTS AND PROCEDURES

Overview

The Schedule of Activities summarizes the frequency and timing of study visits and of immunogenicity and safety measurements applicable to this study.

If multiple assessments are scheduled for the same timepoint, it is recommended that procedures be performed in the following sequence: vital signs, other safety assessments, blood draws. If needed, assessments may be performed at another day within the applicable visit window. Actual dates and times of assessments will be recorded in the source document and/or in the eCRF.

Participants will be provided a thermometer (to measure body temperature), ruler (to measure local injection site reactions), and participant diary to record body temperature and solicited local (injection site) and systemic signs and symptoms.

The participant diary includes instructions on how to capture the data and grading scales to assess severity of the signs and symptoms. The study staff is responsible for providing appropriate training to the participant to avoid missing or incorrect data. The participant diary will be reviewed by the study-site personnel at the visit indicated in the Schedule of Activities.

Over the entire study, approximately 60 mL blood will be collected from each participant to assess humoral immune responses. In addition, approximately 120 mL will be collected from each participant in the Cellular Immuno Subset to assess cellular immune responses. The total blood volume to be collected from participants in the Cellular Immuno Subset will be approximately 180 mL.

Repeat or unscheduled samples may be taken for safety reasons or for technical issues with the samples.

Visit Windows

For the following visits, windows will be allowed as indicated:

Clinic Visit #	Visit Day	Visit Window	Primary Purpose
2	8	$\pm 2 \text{ days}$	7 days after study vaccination, Safety visit, by telephone
3	15	± 3 days	14 days after study vaccination, Immunogenicity and Safety visit
4	29	\pm 5 days	28 days after study vaccination, Safety visit, by telephone
5	183	± 14 days	6 months after study vaccination, Immunogenicity and Safety visit

The timings of the post-vaccination visits will be determined relative to the actual day of vaccination.

Sample Collection and Handling

The actual dates and times of sample collection must be recorded in the eCRF or laboratory requisition form.

Refer to the Schedule of Activities for the timing and frequency of all sample collections.

Instructions for the collection, handling, storage, and shipment of samples are found in the laboratory manual that will be provided. Collection, handling, storage, and shipment of samples must be under the specified, and where applicable, controlled temperature conditions as indicated in the laboratory manual.

Study-Specific Materials

The investigator will be provided with the following supplies:

- IB for Ad26/protein preF RSV vaccine (IB Ad26/protein preF RSV vaccine 2021)
- Study Site Investigational Product and Procedures Manual
- Laboratory manual
- Investigational Product Preparation Instructions
- Participant diary and instructions for use
- Ruler (to measure diameter of any erythema and swelling)
- Thermometer
- Laboratory kits
- Contact Information page(s)
- Study protocol
- IWRS Manual
- Electronic data capture (eDC) Manual/eCRF completion guidelines
- Wallet card
- Sample ICF

8.1. Immunogenicity Assessments

All Participants

For all participants(N 1,113), venous blood samples of approximately 20 mL will be collected for the determination of humoral immune responses at the time points indicated in the Schedule of Activities. Sample collection and processing will be performed by the study-site personnel according to current versions of approved standard operating procedures.

Humoral immunogenicity evaluations are summarized in Table 2. These include exploratory assays that may be performed based on the outcome of other ongoing clinical studies.

Table 2: Summary of Immunogenicity Assays (Humoral)		
Assay	Purpose	
Primary endpoint		
RSV A neutralizing assay (VNA A2)	Analysis of neutralizing antibodies against the RSV A2 strain	
Secondary endpoint		
RSV A pre-F binding antibody (preF	Analysis of antibodies binding to RSV A F protein in pre-fusion form	
ELISA)		
Exploratory endpoints		
RSV strain cross neutralization	Analysis of cross-neutralizing antibodies to RSV B and/or a different	
	RSV A strain(s) using virus neutralization assays and/or other	
	surrogate antibody-binding assays	
Adenovirus neutralization assay	Analysis of neutralizing antibodies to Ad26	
Molecular and functional antibody	Analysis of antibody characteristics including, but not limited to,	
characterization	ADCC, ADCP, avidity, Ig isotype, functional VNAs and binding	
	antibodies to other respiratory viruses, and antibody assessments for	
	antibody repertoire	

ADCC = antibody-dependent cell-mediated cytotoxicity; ADCP = antibody-dependent cellular phagocytosis; ELISA = enzyme-linked immunosorbent assay; Ig = immunoglobulin; VNA = virus neutralization assay.

Cellular Immuno Subset

For a subset of the participants, ie, the Cellular Immuno Subset (N 210), additional venous blood samples of approximately 40 mL will be collected for the determination of cellular immune responses at the time points indicated in the Schedule of Activities. Sample collection and processing will be performed by the study-site personnel according to current versions of approved standard operating procedures.

Cellular immunogenicity evaluations are summarized in Table 3.

Table 3: Summary of Immunogenicity Assays (Cellular)

Assay	Purpose
Exploratory endpoint	
IFN-γ ELISpot	T-cell IFN-γ responses to RSV F protein peptides
Detailed immunoprofiling	Analysis of T-cell responses to RSV F protein peptide-stimulated
	PBMC (including, but not limited to, CD4+/CD8+, IL-2, IFN-γ,
	TNF-α, activation markers and memory) using ICS/cytoF

cytoF = flow cytometry; ELISpot = enzyme-linked immunospot; ICS = intracellular cytokine staining; IFN = interferon; IL = interleukin; PBMC = peripheral blood mononuclear cell; TNF = tumor necrosis factor.

